DryShield vs Cotton Roll Isolation During Sealants Placement: Efficiency and Patient Preference

NCT#: NCT02995369 Protocol ID: 2016-7229 Version Date: 12/7/2016

PI: [name], DMD Program Director Pediatric Dentistry, Department of Dentistry Montefiore Medical Center

Co-PI: [name], DMD Pediatric Dentistry, Department of Dentistry Montefiore Medical Center DryShield vs Cotton Roll Isolation during Sealants Placement: Efficiency and Patient Preference. [name], DMD Pediatric Dentistry Montefiore Medical Center 12/7/16

Elements of Protocol

Introduction and background

In a survey conducted by the National Center for Health Statistics in 2011-2012, approximately 37% of children aged 2–8 years had experienced dental caries in primary teeth. Dental caries among children aged 2–5 was nearly 23% compared with 56% among those aged 6–8. Of children aged 6–11, 21% had experienced dental caries in permanent teeth. Dental caries among children aged 6–8 was nearly 14% and was twice as high for children aged 9–11. Among adolescents aged 12–19, 58% had experienced dental caries in permanent teeth. The prevalence of dental caries experience was higher among adolescents aged 16–19 (67%) compared with those aged 12–15 (50%).¹ Pit and fissure caries account for 80 to 90 percent of all caries in permanent posterior teeth, and 44 percent in primary molars.²

Pit-and-fissure sealants can be used effectively to prevent caries. By micromechanically bonding to the teeth, they provide a physical barrier that keeps microorganisms and food particles from collecting in susceptible pits and fissures, thus preventing caries initiation and arresting caries progression.²

It has been shown that sealants placed on the occlusal surfaces of permanent molars in children and adolescents reduced caries up to 48 months when compared to no sealants. Moreover, their placement reduces caries incidence of 86 percent after one year and 57 percent at 48 to 54 months.³ The effectiveness of sealants for caries prevention depends on long-term retention, which is largely a function of meticulousness of application: keeping the tooth surface free from saliva contamination during application and polymerization is critical⁴. Low retention of sealants has been attributed to insufficient moisture control. ⁵ Therefore, proper isolation of the teeth is one of the most important steps when placing sealants to ensure their retention. ⁶

Several techniques can be used to isolate teeth when applying sealants. The gold standard for isolating teeth has been the rubber dam. However, it often requires the use of a local anesthetic before its placement. Cotton roll isolation (CRI) has been widely used as an alternative to rubber dam isolation for sealant placement, and is the most common method among pediatric dentists. ⁷ CRI requires placing cotton rolls along the buccal mucosa, especially over the parotid glands ducts for maxillary teeth. For the mandibular teeth, the cotton rolls are placed in the buccal vestibule and the floor of the mouth (between the lower buccal mucosa and underneath and/or between the tongue). With this technique, a high-speed evacuation of saliva and water is used. Although very effective, CRI can be a challenging technique especially when used in young children: the cotton rolls can be cumbersome for both the patient and the clinician⁸; additionally, the cotton rolls

have to be changed after and/or during each quadrant as they absorb saliva very quickly.⁶

A previous study demonstrated that new moisture control systems such as Isolite, produce sealant retention rates comparable to cotton roll isolation or rubber dam, while decreasing procedure time.^{6,9} DryShield (DS) has recently been introduced as an all-in-one isolation system. It is similar to the Isolite as it combines the tasks of fluid evacuation, tongue and cheek retraction, and serves as a bite block, but differs in that it's autoclavable and does not provide illumination. Its design allows it to suction and isolate half the oral cavity at a time. Therefore, it should presumably facilitate sealants placement under a more controlled environment, while reducing chair time for the dentist. Colette et al. evaluated patient satisfaction and efficacy of the Isolite during sealant placement, and showed better time efficiency with the Isolite system when compared to cotton roll isolation, some minor discomfort associated with the Isolite, with no significant patient preference for the Isolite or cotton roll isolation.

Research questions/objectives

The goals of this study are to determine if 1) placement times of pit and fissure sealants using the DryShield system differ from those when using the cotton roll isolation technique; and 2) there is a significant difference in patient preference between Dryshield and the cotton roll technique.

Study design

This is a split-mouth, randomized controlled trial study. When patients meeting the inclusion criteria arrive for their sealants application appointment at one of the four pediatric dental clinics of Montefiore, the study protocol will be explained, and patients and parents will be given the option of participating. Once the informed consent has been obtained (patient assent and parental consent), the patients will be randomized into four groups with randomization ratio 1:1:1:1, with each patient acting as their own control. The four groups are a result of randomizing the side receiving one of the interventions (CRI v. DS) as well as the order of application (first v. second). Randomization will be determined using a random number generator in SAS, that will produce envelope inserts with the allocation codes for that subject. Sealed envelopes containing inserts will be labeled with sequential numbers and the next envelope in the sequence will be opened in conjunction with the next subject who qualifies. The four groups are:

Group 1) Sealants placement using CRI on the left side, followed by sealants placement using DS on the right side

Group 2) Sealants placement using CRI on the right side, followed by sealants placement using DS on the left side

Group 3) Sealants placement using DS on the left side, followed by sealants placement using CRI on the right side

Group 4) Sealants placement using DS on the right side, followed by sealants placement using CRI on the left side

One operator will apply all the pits and fissure sealants in a given subject.

Subjects

The target population will include healthy (ASA I/II), deemed able to cooperate children who present to one of the Montefiore pediatric dental clinics for an intake or a recall visit who are determined to benefit from sealants application. or patients who present solely for a sealant application appointment, when their examination was done at a previous date (within 6 months). The sample of patients will range from 5 to 14 years of age. They will be selected based on their cooperative behavior displayed during their visit or recorded at the previous encounter (classified as 3 or 4 according to the Frankl Behavioral Rating Scale). Patients included in the study need to have at least one erupted caries-free permanent molar in each quadrant. Subjects must be able to speak English or Spanish. There will be no exclusions based on race, gender, and ethnicity. Uncooperative, medically compromised patients requiring fewer than four sealants on permanent molars will be excluded. Those who do not provide appropriate assents or consents will be excluded. There are no risks nor benefits for participating in that study. Children participating will only benefit from the sealants application planned as part of their treatment.

Study procedures

When presenting for their scheduled intake or recall appointments, and it has been determined during the examination that the patient would benefit from sealants application, parents of potential subjects meeting the inclusion criteria will be asked if they would like their child to participate in the study. The same will be done for patients coming exclusively for their sealants placement. Informed consents and assents will be obtained at the time of the visit targeted for sealants placement. One operator will apply all the pits and fissure sealants in a given subject with the help of a dental assistant. In each patient, the DS and the CRI will be used to seal maxillary and mandibular molars (either on the left or right side, first or second). The correct size of the autoclavable DS mouthpiece will be picked according to the manufacturer's recommended guidelines.

MOUTHPIECE SIZES

Age Consideration	Dentition Guidelines	Size	
7–8 years of age and younger	Primary or mixed dentition	Pedo	
9 years of age to young teen	Fully-erupted permanent 1 st molars	Small	
Teens to adults	Existing permanent 2 nd molars	Medium	
Adults	Permanent dentition with large vertical opening	Large	

Correct Fit

In the DS group, no other suction device will be used. In the CRI intervention, a Molt mouth prop will be used to help the patients keep their mouth open; an assistant will handle a high-speed suction as well as a saliva ejector.

After the molars are isolated, the technique used for sealant application will be exactly the same for both isolation systems. The teeth will be cleaned using a prophylaxis cup and pumice, rinsed thoroughly, etched with 40% phosphoric acid gel for 15 seconds, rinsed thoroughly, air dried, and sealed with Embrace Wetbond pit and fissure sealant by Pulpdent as per standard protocol, and light cured for 20 seconds. Following placement and curing, the sealants will be checked for proper retention and voids with an explorer. In the case of any voids, defects or material dislodgement, the results will be recorded and the sealant reapplied. The time for sealant application will be recorded with a stopwatch by the dental assistant as follows for the two techniques: the insertion of the isolation aids (DS or CRI) in the oral cavity will constitute the start time, and the end time will coincide with the time when the isolation aids are removed from the oral cavity after the sealants application.

A seven-item survey will be used to evaluate patients' acceptance and satisfaction of CRI and DS. This modified close-ended questionnaire was previously developed and used in a study, which evaluated the efficacy and patient satisfaction associated with the use of Isolite and CRI by Colette et Al. The items will reflect issues of comfort, noise, taste, tissue stretching. The pediatric dental attending will ask the patient each question verbally in the same sequence at the end of the visit.

Patient's preference questionnaire: Cotton roll isolation vs DryShield					
Date: MM/DD/YY					
Child ID:					
Start time of DS: End time of DS:					
Start time of CRI: End time of CRI:					
Randomization Group:					
Please circle the appropriate answer (to be read to subject) :					
1.	Which system made the most noise?	CRI	DS		
2.	Which system stretched your mouth, cheeks, and lips the most?	CRI	DS		
3.	Which system was the most comfortable	CRI	DS		
4.	If we did the procedure again, which system would you prefer?	CRI	DS		
5.	Did either system made you feel as if you needed to gag?	No	Yes		
	If yes, which system made you feel like you needed to gag the most	CRI	DS		
6.	Did you taste any of the materials used?	No	Yes		
	If yes, with which system did you taste the materials the most?	CRI	DS		
7.	Did either system cause any discomfort?	No	Yes		
	If yes, which system caused the most discomfort?	CRI	DS		

Statistical analysis

Estimates of the mean time to completion of the procedure were 398 for CRI and 340 for IS (Collette, 2009). Because the within subject standard deviation was not provided in the Collette 2009 and Lyman 2012 articles, we assumed a standard deviation for the paired/split-mouth design between CRI and IS to be 100 seconds. For an overall α =.05 (as per Lyman) considering two main hypotheses (DS v. CRI; right v. left), then 31 subjects are required for a two-tailed test with 80% power. It is expected that the distribution of differences from right to left, as per a split-mouth randomized design, will be somewhat normally distributed and CRI.

Descriptive statistics will be presented as means and standard deviations for normally distributed data, or medians and ranges if continuous and nonnormal.

Relative frequencies will be presented for dichotomous variables by group, intervention order and side. The statistical analysis is similar to that for a cross-over design in which a side by treatment interaction and first/second application by treatment interaction have to be considered in the analysis. The analysis will be done using a general linear model that accounts for pairing within subject and the interactions described. Preferences for treatment will be presented as proportions along with 95% or 99% confidence intervals as per the predetermined α level.

Implementation plan/timetable

The researcher will perform enrollment of subjects, obtain informed consent and assent, collect data, and perform data entry, management and analysis. Subjects will be enrolled at each of four Montefiore Pediatric Dental Clinics, including [name], [name], [name], and [name]. Numbers will be assigned to each patient to ensure patient privacy and all other identifiers will be removed. Patient enrollment and data collection will begin once IRB approval is obtained

References:

1. National Center for Health Statistics. Center for Disease control and Prevention. Dental Caries and Sealant Prevalence in Children and Adolescents in the United States, 2011-2012.

http://www.cdc.gov/nchs/data/databriefs/db191.htm. Accessed Sept 2016

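### Every device question prints cotton roll before DryShield and naming order is never varied, so a position tendency in the children's answers could shift the preference proportion in all four groups alike

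*Combined protocol and SAP*

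**What the plan says.** The second goal under Research questions/objectives is to find out whether "there is a significant difference in patient preference between Dryshield and the cotton roll technique". The instrument is the questionnaire under Study procedures, and the direct preference question is item 4: "If we did the procedure again, which system would you prefer".

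- **Layout.** One form is shown. Items 1 to 4 and the follow-ups to items 5, 6 and 7 (the last being "If yes, which system caused the most discomfort") make seven device choices. All seven print CRI first and DS second. Items 1 to 4 have no answer for a child who sees no difference.
- **Delivery.** The form is marked "to be read to subject", and "The pediatric dental attending will ask the patient each question verbally in the same sequence at the end of the visit". This fixes the order of the questions. It does not say how, or in what order, the two options are spoken.
- **Randomisation.** Under Study design, the four groups come from "randomizing the side receiving one of the interventions (CRI v. DS) as well as the order of application". The SAS generator will "produce envelope inserts with the allocation codes for that subject". Naming order is not part of the allocation.
- **Analysis.** Under Statistical analysis, preferences are reported as proportions with a 95% or 99% interval. The section also says: "Relative frequencies will be presented for dichotomous variables by group, intervention order and side". No term or tabulation involves naming order.

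**The concern.** A child with no real preference must still choose a device on item 4. If some of these children tend to pick whichever option they hear first, or last, a fixed naming order turns that habit into an apparent preference for one device.

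The four-group design does not protect against this. It balances side and order of application, but if options are read as printed the naming order is CRI then DS in every group. Averaging over groups therefore leaves the shift in place. Because naming order never varies, no analysis can estimate or remove it afterwards, and the confidence interval does not allow for it.

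Attendings might instead name the devices in the order in which they were used. The overall proportion would then be nearly balanced, but naming order would coincide with application order, and a position tendency would appear as an order effect in the planned by-order frequencies. The form has no field to show which practice was followed.

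**Working it through.** **Inputs from the documents.** Sample size 31; four groups at 1:1:1:1; preference reported as a proportion with a 95% or 99% interval, no interval method named. The sample size was set for placement time and reproduces: a paired t-test with difference 398 − 340 = 58, SD 100 and two-sided alpha 0.05/2 = 0.025 needs n = 31 (power 0.803). The plan gives no figure for preference, so there is none to reproduce there.

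**Assumed inputs.** A share f of children is indifferent (20% to 40%), and a share q of those picks one given position (65% to 75%). Neither comes from the documents. The tendency is taken to have the same sign in all four groups.

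**Size of the shift.** Bias b = f × (q − 0.5):

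- 0.2 × 0.15 = 0.03, or 0.03 × 31 = 0.9 children
- 0.3 × 0.20 = 0.06, or 1.9 children
- 0.4 × 0.25 = 0.10, or 3.1 children

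For comparison, the 95% half-width at n = 31 is 1.96 × √(0.25/31) = 0.176.

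**Chance of wrongly excluding 50%.** Suppose there is no true preference, and the number choosing the favoured position is binomial with n = 31 and p = 0.50 + b. Because the method is unnamed, exact (Clopper-Pearson) and Wilson or Wald intervals are both shown.

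| Interval | Excludes 50% at | b = 0 | b = 3 points | b = 6 points | b = 10 points |
|---|---|---|---|---|---|
| Exact 95% | ≤9 or ≥22 | 2.9% | 3.9% | 6.7% | 14.4% |
| Wilson or Wald 95% | ≤10 or ≥21 | 7.1% | 8.6% | 13.4% | 24.7% |
| Exact 99% | ≤7 or ≥24 | 0.3% | 0.5% | 1.1% | 3.3% |
| Wilson or Wald 99% | ≤8 or ≥23 | 1.1% | 1.5% | 3.0% | 7.4% |

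At 3 points the effect is smaller than the difference between interval methods.

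**Two form versions alternated within each group.** Each group can be out of balance by at most one child. Since 31 is odd, at most three of the four groups can have an odd count, so the worst overall split is 17/14. The residual bias is b × 3/31, which is 0.29, 0.58 and 0.97 points for b = 3, 6 and 10. The 95% exclusion rate is then 2.7% to 2.9% (exact) or 6.7% to 7.0% (Wilson or Wald), no higher than with no bias.

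**Options voiced in order of use.** If CRI-first and DS-first children split 16/15, the overall residual is b/31, or 0.10, 0.19 and 0.32 points. The by-order contrast, however, carries 2b, or 6, 12 and 20 points.

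**Can two versions measure the tendency?** Not usefully. The between-version contrast has 95% half-width 1.96 × √(0.25/16 + 0.25/15) = 0.352, against a signal of 2b = 6, 12 or 20 points. Approximate power is 6%, 10% and 20%.

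**The case against.** The strongest reply is that the harm needs two unknowns together: the attending must voice the options in printed order, and a net position tendency must exist. The question texts name no device and the answer cells are clinicians' abbreviations, so the attending may well describe the devices in other words and another order. Item 4 also follows three direct comparisons made at the same visit, so 40% indifference may be too high. The larger error rates come only from the extreme of the assumed range and from exactly no true preference. All of this stands. It makes the finding conditional and small, but a fixed naming order still leaves the trial unable to tell whether the tendency was there.

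A second reply is that one sentence telling attendings to name devices in order of use would protect the overall proportion as well or better: 0.10 to 0.32 points of residual, against 0.29 to 0.97 for two forms. That is correct for a 16/15 split. The protocol states no blocking, however. With simple randomisation, a one-SD imbalance of √31 ≈ 5.6 children gives b × 5.6/31, about 0.5 to 1.8 points. More importantly, this route mixes naming order with application order, a factor by which the plan intends to report.

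Third, two forms do not remove position answering. Indifferent children still have to choose, and a real preference is pulled slightly towards 50%. This also stands: the remedy cancels the directional shift only.

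Finally, the questionnaire is adapted from one used in an earlier study. The documents do not say that option order was examined there, so earlier use does not settle the point.

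**Conclusion.** The concern holds as a minor, conditional weakness in how one of the two study goals is measured. The layout, the unscripted voicing and the absence of naming order from the randomisation are plain in the text. If options are read as printed, a position tendency with the same sign in every group would shift the item 4 proportion in one direction, and could be neither detected nor corrected.

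Whether such a tendency exists, and its size and direction, are unknown. The illustrated 3 to 10 points rest wholly on assumed indifference and position-following, and even the upper end lies within sampling error at n = 31. This is not a demonstrated bias in the preference result. The sample size and the placement-time comparison are unaffected.

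**What to change.** Print two versions of the questionnaire, one naming CRI first and one naming DS first throughout. Alternate them within each of the four randomisation groups by adding the version to the code on the existing envelope insert. State that the attending reads the options in printed order, and record the version on the form. This approximately cancels any directional shift in the overall item 4 proportion and keeps naming order separate from application order.

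Do not present the difference between versions as an estimate of the position effect; 31 children are too few for that.

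The cost is a second printed form, one more code on the insert and one more recorded field. Subjects may speak English or Spanish, so if the form is translated there would be four printed versions rather than two. Question wording, question sequence and sample size stay as they are.

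### Half of the overall alpha appears to be spent on a right v. left comparison that is not a study goal; giving it all to DryShield v. cotton rolls lifts power for time from 80% to about 88% at the same N

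*Combined protocol and SAP*

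**What the plan says.** Research questions/objectives lists two goals without ranking them. The first is whether "placement times of pit and fissure sealants using the DryShield system differ from those when using the cotton roll isolation technique"; the second is whether "there is a significant difference in patient preference between Dryshield and the cotton roll technique".

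The sample-size paragraph of Statistical analysis takes mean times of 398 (cotton rolls) and 340 (a similar device) from an earlier study. No within-subject SD was available, so "we assumed a standard deviation for the paired/split-mouth design between CRI and IS to be 100 seconds". It then sets an overall alpha of .05 and, "considering two main hypotheses (DS v. CRI; right v. left), then 31 subjects are required for a two-tailed test with 80% power". It does not state the level for each hypothesis.

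Under Study design, side and order are randomised together in four groups, 1:1:1:1. For the general linear model, Statistical analysis says that "a side by treatment interaction and first/second application by treatment interaction have to be considered in the analysis".

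On preference it says: "Preferences for treatment will be presented as proportions along with 95% or 99% confidence intervals as per the predetermined" alpha level. It names no item, test or power. The form in Study procedures has seven items under the title "Patient's preference questionnaire: Cotton roll isolation vs DryShield". Only item 4 asks which system the child would prefer if the procedure were repeated.

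**The concern.** The hypotheses that share the alpha are not the goals. Right v. left answers neither goal, yet it counts as one of two main hypotheses. Preference is a goal, but no alpha, test or power is assigned to it.

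For time, the stake is efficiency. If half of .05 goes to side, the comparison that the trial exists to make is tested more strictly than it needs to be. Its power then rests on an SD that the plan itself calls assumed, with almost no margin.

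For preference, the stake is smaller. Two interval levels are written, and at a few possible results they give different answers on whether the preferred share differs from 50%.

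**Working it through.** **Inputs.** From Statistical analysis: difference 398 − 340 = 58, read as seconds (the unit of the SD); SD of the paired differences 100 s; two-tailed; 80% power; overall alpha .05. Standardised difference: 58/100 = 0.58.

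**Method.** Paired t-test, n − 1 df, noncentrality 0.58 × √n, exact noncentral t.

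**Reproducing the plan's 31.**

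| Two-sided level for time | Power one below the smallest N | Smallest N for 80% |
|---|---|---|
| 0.05 | n=25: 79.5% | 26 (81.1%) |
| 0.05/2 = 0.025 | n=30: 78.7% | **31 (80.3%)** |
| 0.01 | n=38: 79.9% | 39 (81.2%) |

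Of these levels, only 0.025 gives 31. The normal approximation, ((z for the level + z for 80% power)/0.58)², gives 28.26 at 0.025, so 29, and 23.33 at 0.05, so 24. The side hypothesis therefore accounts for 31 − 26 = 5 children.

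**Keeping N=31 and testing time at 0.05.** The noncentrality is 0.58 × √31 = 3.229. The critical t on 30 df falls from 2.360 to 2.042, and power rises from 80.3% to 87.8%, a gain of 7.5 points.

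**Margin on the assumed SD (N=31).** 80% power holds up to 100.3 s at 0.025 and up to 111.5 s at 0.05. At an SD of 111.5 s, power at 0.025 would be about 70%.

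**Terms for side and order.** With 28 error df in place of 30, N=31 gives 80.0% at 0.025 and 87.6% at 0.05, and the largest SD at 0.05 is 111.3 s. The conclusion does not change.

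**Preference: when does the interval level matter?** Exact (Clopper-Pearson) intervals, all 31 children answering item 4:

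| Count choosing one system | 95% interval | 99% interval |
|---|---|---|
| 21/31 | 48.6–83.3% | 43.1–86.8% |
| 22/31 | 52.0–85.8% | 46.4–89.0% |
| 23/31 | 55.4–88.1% | 49.8–91.0% |
| 24/31 | 58.9–90.4% | 53.3–93.0% |

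The level decides whether 50% is excluded only at 22 and 23, and at the mirror counts 8 and 9. The binomial probability of these four counts depends on the true share, which is an assumption here:

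| True share | 50% | 55% | 60% | 70% | 75% | 80% |
|---|---|---|---|---|---|---|
| Probability | 2.6% | 4.7% | 11.1% | 29.7% | 29.8% | 19.5% |

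**Power for preference.** The exact two-sided test at 0.05 needs at least 22/31 (or at most 9/31). Power is 54.2% at a true share of 70% and 77.1% at 75%; 80% power needs about 76%. If preference is tested only after time is significant, and the two results are taken as independent (an assumption), the chance of both is 0.878 × 0.542 = 48% at 70% and 0.878 × 0.771 = 68% at 75%.

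**The case against.** **The sizing contains no error.** The plan openly states an overall alpha, two hypotheses and N=31. In a split-mouth trial that randomises side, testing side is a defensible and conservative choice, and the plan never writes 0.025. This stands. A reader might infer that 31 is wrong, that time is underpowered or that type I error is inflated, but the documents support none of these. What remains is that a comparison outside the goals costs power that can be recovered without more children.

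**The planned model does not exactly cover right v. left.** The text names side-by-treatment and order-by-treatment interactions, not a side main effect. This stands as a point of wording, so the fix asks for side and order terms explicitly. Numerically it matters little (87.6% against 87.8%).

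**The preference analysis is less open than it looks.** The interval is tied to the predetermined alpha, and the only alpha written is .05, which points to 95%. Item 4 is the only question that asks directly about preference. No rule says that excluding 50% decides goal 2, although the word 'significant' in that goal suggests one. This largely stands. A reader might infer that any of the seven items could serve as the preference outcome, or that the level is likely to change the answer. A form title does not turn noise, gagging or taste into preference outcomes. The earlier study of a similar device is reported "with no significant patient preference for the Isolite or cotton roll isolation", which makes shares near 50% plausible, and there the level matters in only 3–5% of trials. No passage supports the 70–75% share at which it matters in about 30%.

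**Preference should not be demoted.** The two goals are listed side by side, so the documents do not support simply relabelling preference as secondary. This stands, and the fix offers a way to keep it as a tested goal.

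**Conclusion.** The point holds as an inexpensive improvement to the time analysis. The main hypotheses do not match the goals, and the right v. left hypothesis costs about 8 points of power at N=31, or equivalently 5 of the 31 children. This rests on the plan's 58 s and 100 s, a paired t-test, and an equal alpha split that is inferred because it reproduces 31 exactly. The plan is valid as it stands.

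The preference part is a minor clarification. One interval level and one named item would remove an ambiguity that affects four of the 32 possible counts (0 to 31). The plan should also say that power for preference at N=31 is modest.

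**What to change.** In the sample-size paragraph of Statistical analysis:

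1. Remove right v. left from the main hypotheses. State that side and order are terms in the general linear model without a share of alpha.
2. Keep N=31, test DryShield v. cotton-roll time at two-sided 0.05, and restate power as about 88% for 58 s and an SD of 100 s, with 80% holding up to an SD of about 111 s.

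In the preference sentence:

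3. Name item 4 as the preference item, compare it with 50%, and delete the 99% option so that one exact 95% interval is reported.
4. To keep preference as a tested goal within the overall .05, test it at two-sided 0.05 only after time is significant (fixed sequence). If the sponsor does not want this, label it descriptive.
5. State the power for preference at N=31: 54% at a true share of 70% and 77% at 75%, before allowing for the time test that precedes it.

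**Cost.** Wording in two paragraphs and no extra children. A right v. left difference is reported as an estimate with its interval and no longer as a main test. Under the fixed sequence, no confirmatory claim on preference is possible if time is not significant.

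### Does offering a 95% or 99% interval for patient preference, outside the hypotheses named under the overall alpha, leave goal 2 without a usable error level?

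*Combined protocol and SAP*

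**What the plan says.** Under Research questions/objectives the plan has two goals. The first is whether "placement times of pit and fissure sealants using the DryShield system differ from those when using the cotton roll isolation technique". The second is whether "there is a significant difference in patient preference between Dryshield and the cotton roll technique".

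The sample-size paragraph of Statistical analysis sets the error rate: "For an overall α =.05", "considering two main hypotheses (DS v. CRI; right v. left"). It concludes that "31 subjects are required for a two-tailed test with 80% power". The inputs are procedure times, so this alpha belongs to the time comparison.

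The same section ends with preference: "Preferences for treatment will be presented as proportions along with 95% or 99% confidence intervals as per the predetermined α level". No test is named for it, and neither is a null value or an interval method. Item 4 of the questionnaire under Study procedures asks the question directly: "If we did the procedure again, which system would you prefer".

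**The concern.** Three things do not fit together. Side is not a goal, yet it is named under the overall alpha; preference is a goal, yet it is not. One predetermined alpha cannot yield two alternative confidence levels. And 99% corresponds to an alpha of 0.01, which appears nowhere in the plan.

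Goal 2 asks about a significant difference, so the level decides whether an interval excludes 50%. If the choice were left until the data were in, an analyst could pick the level that gave the preferred conclusion and still claim to have followed the text. It is also unclear whether a positive preference result counts within the overall 0.05 or in addition to it.

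**Working it through.** **1. The plan's own figure.** Inputs from Statistical analysis: mean times 398 and 340, so a difference of 398 − 340 = 58 seconds; SD of the paired difference 100 seconds; two-tailed; 80% power. For a paired t-test, power is the probability that |T| exceeds t(1 − α/2, n − 1), where T is noncentral t with n − 1 degrees of freedom and noncentrality 0.58 × √n.

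| α per hypothesis | n for 80% power | Power at n = 31 | Matching interval |
|---|---|---|---|
| 0.05 | 26 | 87.8% | 95% |
| 0.05/2 = 0.025 | 31 | 80.3% | 97.5% |
| 0.05/3 = 0.0167 | 35 | 75.2% | 98.3% |
| 0.01 | 39 | 68.2% | 99% |

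The 31 subjects reproduce at 0.025, that is, 0.05 split over the two named hypotheses. The 0.025 is inferred, not written. The stated alpha gives 95%, the inferred one 97.5%, and neither gives 99%.

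**2. Where the level matters.** Assumptions: all 31 children answer item 4, and the null is 50%. Exact two-sided binomial p-values are 0.071 at 21 of 31, 0.029 at 22, 0.011 at 23 and 0.003 at 24. Exact (Clopper-Pearson) intervals:

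| Count | 95% | 97.5% | 99% |
|---|---|---|---|
| 22/31 (71%) | 52.0–85.8% | 49.4–87.3% | 46.4–89.0% |
| 23/31 (74%) | 55.4–88.1% | 52.8–89.5% | 49.8–91.0% |

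By symmetry, 95% and 97.5% disagree only at 22 or 9, and 95% and 99% only at 22, 23, 9 or 8.

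**3. How often that happens.** Binomial probability of those counts with n = 31, exact intervals:

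| True preference | 95% v. 97.5% | 95% v. 99% |
|---|---|---|
| 50% | 1.9% | 2.6% |
| 55% | 3.2% | 4.7% |
| 60% | 7.0% | 11% |
| 65% | 12% | 21% |
| 70% | 16% | 30% |
| 75% | 14% | 30% |
| 80% | 7.6% | 20% |

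**4. Dependence on the interval method.** The plan names none, so the boundary counts are not fixed. With Wilson intervals 21/31 gives 50.1–81.4% at 95% and 47.6–82.9% at 97.5%, while 22/31 gives 50.8–85.2% at 97.5%. The 95% versus 97.5% disagreement therefore moves to 21 or 10; Wald intervals behave the same way. The size of the problem is similar, but the counts differ.

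**5. The trade-off over sharing alpha.** Keeping preference outside the 0.05 makes the nominal total 0.025 + 0.025 + 0.05 = 0.10. Bringing it in at 0.025 lowers power at a 70% true preference from 54% to 39% with exact intervals, or from 69% to 54% with Wilson or Wald. The preference needed for 80% power rises from about 76% to 79% (exact), or from about 73% to 76% (Wilson or Wald). An equal three-way split would take the time comparison to 35 subjects, or leave it at 75% power with 31.

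**The case for a change.** The strongest case for a change is that goal 2 is worded as a significance question and the plan prints a second level beside the natural one. At true preferences of 60% to 80%, the two printed levels lead to opposite conclusions 11% to 30% of the time with exact intervals. One sentence would settle it, at no cost in subjects.

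The observation about the wording stands: the 99% option has no source in the plan. The 11% to 30% range, however, applies only if an analyst departs from the one stated alpha and uses a level that nothing supports. The background says of the similar device that the comparison study ended "with no significant patient preference for the Isolite or cotton roll isolation". That does not show a true preference near 50%, so I do not use it to dismiss the higher figures.

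It is also fair to say that calling preference purely descriptive goes too far, given how goal 2 is phrased. But the analysis text promises proportions with intervals, not a confirmatory test. Reading preference as outside the sample-size alpha is therefore reasonable.

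**Conclusion.** No change is needed. The 99% option is a slip of wording. The sentence ties the interval to the predetermined alpha, the only one stated is 0.05, and that gives 95%. An analyst following the text reaches a usable answer to goal 2 from item 4 without further instruction. The result is a single count out of at most 31, so a reader who wants a stricter level can recompute the interval from the reported proportion and the number answering.

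Whether preference should share the overall 0.05 is a fair trade-off, not an error: a nominal total of 0.10 on one side, a loss of about 15 percentage points of power at a 70% preference on the other. Neither reading affects the time analysis, and 31 subjects remain correct for it at 0.025 per hypothesis.

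The residual exposure is one pair of counts between 95% and 97.5%: 22 or 9 with exact intervals, 21 or 10 with Wilson or Wald. With exact intervals its probability runs from 1.9% at a true preference of 50% to about 16% near 70%. These figures assume 31 complete answers and a 50% null, neither of which the plan states for preference.
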